4.2.3. Visit 3 (Month 4) +/- 4 days

Subjects will continue to take BLI400 daily and will return to the clinic for Visit 3 (Day 120). Vital signs (See [section 4.1](#) for details) will be recorded. Study personnel will weigh returned bottles and count rescue bisacodyl for accountability purposes. Subjects will be queried for any adverse events or changes to their concomitant medications. Subjects will complete the PAC-QOL and PAC-SYM questionnaires. Samples for chemistry, hematology and urinalysis will be repeated as outlined in [Section 4.1](#). Subjects will be dispensed 2 new bottles of study medication. Subjects will be instructed to return all bottles and bisacodyl at the next follow up visit.

4.2.4. Visit 4 (Month 6) +/- 4 days

Subjects will continue to take BLI400 daily and will return to the clinic for Visit 4 (Day 180). Vital signs (See [section 4.1](#) for details) will be recorded. Study personnel will review returned bottles and rescue bisacodyl for accountability purposes. Subjects will be queried for any adverse events or changes to their concomitant medications. Subjects will complete the PAC-QOL and PAC-SYM questionnaires. Samples for chemistry, hematology and urinalysis will be repeated as outlined in [Section 4.1](#). Subjects will be dispensed 3 new bottles of study medication. Subjects will be instructed to return all bottles and bisacodyl at the next follow up visit.

4.2.5. Visit 5 (Month 9) +/- 4 days

Subjects will continue to take BLI400 daily and will return to the clinic for Visit 5 (Day 270). Vital signs (See [section 4.1](#) for details) will be recorded. Study personnel will review returned bottles and rescue bisacodyl for accountability purposes. Subjects will be queried for any adverse events or changes to their concomitant medications. Subjects will complete the PAC-QOL and PAC-SYM questionnaires. Samples for chemistry, hematology and urinalysis will be repeated as outlined in [Section 4.1](#). Three new bottles of study medication will be dispensed at this visit. Subjects will be instructed to return all bottles and bisacodyl at Visit 6.

4.2.6. Visit 6 (Month 12 or Early Term) +/- 4 days

Subjects will return at Day 360 for their final clinic visit. Vital signs (see [section 4.1](#) for details) and ECGs will be recorded. A physical examination will be performed.

Study

Braintree Laboratories, Inc.
Protocol Number BLI400-303

Confidential

personnel will weigh returned bottles and count bisacodyl for accountability purposes. Subjects will be queried for any adverse events or changes to their concomitant medications. Subjects will complete the PAC-QOL and PAC-SYM questionnaires. Samples for chemistry, hematology and urinalysis will be repeated as outlined in [Section 4.1](#). Clinically significant laboratory abnormalities present at Visit 6 should be followed until resolved or are considered stable.

4.2.7. Follow-up Telephone Call (*Day 374*) +/- 4 days

At Day 374, approximately 2 weeks after the last study visit or early term visit, site personnel will contact subjects by telephone to query if any new adverse events have occurred and if any adverse events ongoing at Visit 6 have resolved. Subjects will also be asked about the status of their concomitant medications.

Braintree Laboratories, Inc.
Protocol Number BLI400-303

Confidential

4.3. Tabulated Study Procedures

The following graphically depicts the flow of study procedures at each visit.

Procedures	Visit 1 Day 0	Visit 2 Month 2 +/- 4 days	Visit 3 Month 4 +/- 4 days	Visit 4 Month 6 +/- 4 days	Visit 5 Month 9 +/- 4 days	Visit 6 Month 12/ ET +/- 4 days	☞ Day 374 +/- 4 days
Informed Consent	X						
Inclusion/Exclusion Criteria Review	X						
Medical History	X						
Physical Examination	X					X	
Vital Signs ¹	X	X	X	X	X	X	
Electrocardiogram	X	X				X	
Review of Concomitant Medication	X	X	X	X	X	X	X
Urine Pregnancy Test (if applicable) ²	X						
Enroll Eligible Subjects	X						
Subject to Complete PAC-QOL, PAC-SYM	X	X	X	X	X	X	
Blood Sample for Chemistry Testing	X	X	X	X	X	X	
Blood Sample for Hematology Testing	X	X	X	X	X	X	
Urine Sample for Urinalysis	X	X	X	X	X	X	
Blood Sample for Serum Pregnancy Testing				X		X	
Dispense Study Drug and Rescue Bisacodyl	X	X	X	X	X		
Study Drug and Rescue Bisacodyl Accountability		X	X	X	X	X	
Assess Safety		X	X	X	X	X	X

¹blood pressure and pulse while seated and after standing for 2 minutes, temperature, weight and height (@Visit 1

²only) refer to [Section 4.4](#)

4.4. Pregnancy

Subjects who are female and of childbearing potential must have a urine pregnancy test done at screening. A positive result will rule out the participation of the subject in the study. Serum pregnancy tests will be performed at Visits 4 (Month 6) and 6 (Month 12). If a subject becomes pregnant during the study, the subject must be removed from the study and followed until one month after the end of the pregnancy.

Female study subjects must be surgically sterilized or using oral contraceptives, depot contraceptives, double-barrier method, intrauterine device, or testifies that she is monogamous with a vasectomized partner. Subjects practicing abstinence must agree to use an acceptable form of birth control should they become sexually active during the study.

Women with a history of bilateral tubal ligation are not considered of childbearing potential and are not required to have a urine pregnancy test at screening.

Oral contraceptives, hormone implants, and injections are only considered effective if started at least 1 month before the study.

Menopausal status is defined when menses have been absent for 12 months in a woman of appropriate age (usually 45 to 55 years) who has no other suspected or identified cause of amenorrhea.

4.5. Concomitant Medications

The use of concomitant medication will be recorded from 7 days prior to Visit 1 until the end of the study at the telephone contact on Day 374. Subjects enrolled in this study will not be permitted to take any laxatives (other than the sponsor supplied rescue bisacodyl), whether prescription or over-the-counter, from Visit 1 until after completion of Visit 6. Any restricted laxative use during the study may result in termination of subject's participation. Subjects may not initiate treatment with any constipating medication.

5. ADVERSE EVENTS

5.1. Adverse Event Definition and Reporting

An Adverse Event (AE) is any untoward medical occurrence associated with the use of a drug in humans, whether or not considered drug related. An AE can therefore be any unfavorable and unintended sign (including a clinically significant abnormal laboratory finding), symptom, or disease temporally associated with the use of a medicinal (investigational) product.

Adverse event collection will coincide with the subject providing informed consent to participate in the study and will conclude with the end of study participation at Day 374 Follow-up Call. Diarrhea should be reported as an adverse event if a subject has more than 3 watery stools per day. Subjects with clinically significant laboratory results at Visit 6 which are classified by the Investigator as adverse events should return for a repeat blood draw. Subjects will be instructed to report promptly adverse events to the Investigator. The Investigator will record date/time of report, date/time of onset, description of the adverse event, severity of adverse event, action(s) taken regarding treatment of the event, action(s) taken regarding study participation, duration of adverse event, and the Investigator's assessment of relationship of adverse event to study treatment.

The Investigator should assess the severity of each adverse event using the following categories:

Grade	Severity	Description
1	Mild	Barely noticeable, does not influence functioning Causing no limitations of usual activities
2	Moderate	Makes participant uncomfortable, influences functioning Causing some limitations of usual activities
3	Severe	Severe discomfort, treatment needed Severe and undesirable, causing inability to carry out usual activities
4	Life threatening	Immediate risk of death Life threatening or disabling
5	Fatal	Causes death of the participant

Braintree Laboratories, Inc.
Protocol Number BLI400-303

Confidential

The Investigator should assess the relationship to study drug for each adverse event using the following categories:

Categories of Attribution:	Description
UNRELATED	There is no evidence of any causal relationship.
POSSIBLE	There is some evidence to suggest a causal relationship (e.g., the event occurred within a reasonable time after administration of the trial medication). However, the influence of other factors may have contributed to the event (e.g., the patient's clinical condition, other concomitant events).
PROBABLE	There is evidence to suggest a causal relationship, and the influence of other factors is unlikely .
DEFINITE	There is clear evidence to suggest a causal relationship, and other possible contributing factors can be ruled out .

In published Phase 3 studies, adverse events associated with BLI400 administered at doses required for effective treatment of constipation included flatulence, nausea, vomiting, abdominal cramping or pain and bloating. These adverse reactions were transient and subsided rapidly upon dose adjustment or cessation.

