3.4. Study Treatments

BLI400 Laxative

BLI400 laxative will be provided polyethylene bottles containing sufficient study medication for 30 days of dosing. The bottles will be equipped with a cap that can be used to measure 10.5 grams of BLI400. Each bottle will also have a clinical label containing a caution statement, study code, study sponsor and subject number. Subjects will be instructed to mix the contents of 2 capfuls (approximately 21 g) in 4 - 8 oz of juice or other beverage, and take once daily preferably in the morning. Subjects that develop persistent diarrhea or loose stools will be allowed to adjust their dose down to 10.5g (1 capful) per day.

Rescue Bisacodyl

Subjects will be dispensed bisacodyl at each study visit (previously dispensed bisacodyl may be redispensed if needed, although this is not encouraged). Subjects will be instructed to take 5 – 10mg (1 – 2 tablets) of bisacodyl if they are experiencing severe discomfort due to their constipation, or have not had a BM in 4 days. No more than 6 tablets (30mg) of bisacodyl should be taken in a week.

If a subject does not have a bowel movement within 24 hours of taking a bisacodyl dose, a second dose should be taken. If after the second bisacodyl dose the subject does not have a BM within 24 hours, the subject should contact the site. The investigator should then consider having the subject return for an evaluation and/or discontinuing the subject from the study.

All study medication is required to remain at room temperature 20°-25°C (68°-77°F); excursions permitted between 15°-30°C (59°-86°F).

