4.2. Treatment Period

4.2.1. Treatment Day 1

Starting on the morning of Treatment Day 1 (the day after Visit 1), subjects will measure 2 capfuls of study medication and ingest it mixed in a beverage of their choice. Subject will take a daily dose of 2 capfuls until they return for Visit 2. Subjects that develop persistent diarrhea or loose stools should contact their study center. These subjects will be allowed to adjust their dose down to 10.5g (1 capful) per day.

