4.2.2. Visit 2 (*Month 2*) +/- 4 days

Subjects will continue to take BLI400 daily and will return to the clinic for Visit 2 (Day 60). Vital signs (see [section 4.1](#) for details) and ECGs will be recorded. Study personnel will weigh returned bottles and count rescue bisacodyl for accountability purposes. Subjects will be queried for any adverse events or changes to their concomitant medications. Subjects will complete the PAC-QOL and PAC-SYM questionnaires. Samples for chemistry, hematology and urinalysis will be repeated as outlined in [Section 4.1](#). Subjects will be dispensed 2 new bottles of study medication. Subjects will be instructed to return all bottles and bisacodyl at the next follow up visit.

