9.3.2. Safety Analyses

Analysis of safety will be performed using the modified Intent to Treat population (see [Section 9.4](#)).

Adverse Events

Adverse Events will be coded using the MedDRA classification to provide a preferred term and primary system organ class for each event. Proportions of subjects with adverse events will be presented for the overall study population, and each demographic subgroup (age, gender and race). Tables of AEs will be presented by system organ class and preferred term, and include overall totals for AEs within each system organ class. Counting will be done by subject and not by event. A table of counts and percentages will also be made of those subjects with SAEs or AEs which led to withdrawal from the study.

Treatment-emergent AEs are defined as adverse events that had an onset day and time on or after the day and time of the first dose of study drug until the Day 374 Follow-up Call. Adverse Events having missing onset dates will be considered as treatment emergent.

The difference in adverse event rates between study periods will be tested by Chi-Square or Fisher's exact test with 95% confidence intervals.

Laboratory Parameters

Summary statistics (i.e., mean, minimum, maximum, standard deviation, and number of subjects) will be presented for each laboratory parameter at each visit. Laboratory data will be summarized for the overall population and the elderly and non-elderly subgroups. When calculating the summary statistics only, the last observation within a visit window will be used if there are multiple observations. Changes from baseline (Visit 1) will be presented in a similar format. An additional listing will be provided of those subjects who have clinically significant laboratory values. The data will also be presented as shift tables and clinically significant abnormalities will be examined.

Results of laboratory tests for the change from baseline (Visit 1) and group differences will be tested using ANOVA.

Vital Signs

Summary statistics (i.e., mean, minimum, maximum, standard deviation, and number of subjects) will be presented for each vital sign at each visit and compared to the values obtained at Visit 1. When calculating the summary statistics only, the last observation within a visit window will be used if there are multiple observations. The data will also be presented as shift tables and clinically significant abnormalities will be examined.

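### Loose stools can justify halving the dose without meeting the diarrhea reporting rule, and no dose-reduction summary is planned, so some dose-limiting cases may be missing from the AE tables

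*Combined protocol and SAP*

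**What the plan says.** Three provisions of the protocol bear on this. The second copy in the combined document repeats them.

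- **Dose reduction.** Section 3.4: "Subjects that develop persistent diarrhea or loose stools will be allowed to adjust their dose down to 10.5g (1 capful) per day". Section 4.2.1 repeats the permission and adds: "Subjects that develop persistent diarrhea or loose stools should contact their study center".
- **Reporting of diarrhea.** Section 5.1: "Diarrhea should be reported as an adverse event if a subject has more than 3 watery stools per day".
- **General AE definition.** Also in 5.1: "An AE can therefore be any unfavorable and unintended sign (including a clinically significant abnormal laboratory finding), symptom, or disease temporally associated" with use of the product.

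For each AE, the investigator records, among other items, "action(s) taken regarding treatment of the event, action(s) taken regarding study participation". On the analysis side, the only action-based AE summary is in 9.3.2: "A table of counts and percentages will also be made of those subjects with SAEs or AEs which led to withdrawal from the study". Section 9.3 describes no summary of dose reductions or of the dose actually taken.

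**The concern.** Two thresholds for the same symptom operate side by side, and the one that changes treatment is the lower. A numeric cut-off that separates expected laxative effect from an adverse event is defensible in itself. The difficulty comes when a symptom below the cut-off has been troublesome enough to halve the dose and the plan does not say that it must be recorded.

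Safety is the sole objective (Section 2), there is no control arm, and Section 9.1 justifies 300 subjects by the wish to see events that become more frequent or more severe with time. Section 9.3.2 also compares AE rates between study periods. If dose reductions and their causes go unrecorded, the AE tables may leave out tolerability failures. Later periods would also mix 21 g and 10.5 g exposure with no table to show it.

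**Working it through.** **Step 1. Is there a figure to reproduce?** No. The 300 in Section 9.1 is an exposure number taken from a guideline. The documents give no diarrhea rate and no dose-reduction rate. The check is therefore a comparison of the provisions, followed by an illustration.

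**Step 2. The rules side by side, for stools that persist.**

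| Stool pattern | Dose may be halved (3.4, 4.2.1) | Diarrhea rule (5.1) | General AE definition (5.1) |
|---|---|---|---|
| Loose, not watery | Yes | Not met | Left to judgement |
| Watery, 1 to 3 a day | Yes | Not met | Left to judgement |
| Watery, above 3 a day | Yes | Met, so reported | Not needed |

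In the first two rows treatment may change while the entry of an AE is left to the investigator.

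**Step 3. Does anything else in the plan recover those rows?**

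- The actions taken (5.1) are attached to an event already entered as an AE. A change in study-drug dose is not named among them.
- The action-based table in 9.3.2 covers SAEs and AEs leading to withdrawal, not those leading to dose reduction.
- Returned bottles are weighed for accountability at Visits 2, 3 and 6, and reviewed at Visits 4 and 5. Weight alone cannot tell a halved dose from missed doses.
- PAC-SYM has no item on loose or watery stools. PAC-QOL has none either. Its item 11 concerns embarrassment at frequent bathroom visits away from home. Both look back two weeks only.
- No stool diary is described. Visits fall on Days 60, 120, 180, 270 and 360, so they are 60 to 90 days apart.

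None of these sources would identify the cases or give their reasons.

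**Step 4. Illustration of size; both rates are assumed.** Let p be the share of subjects who reduce the dose for diarrhea or loose stools. Let s be the share of those whose symptom stays at or below the diarrhea threshold and is not entered as an AE.

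Expected number missing = 300 × p × s

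| p | Subjects reducing dose (300 × p) | s = 0 | s = 25% | s = 50% | s = 75% |
|---|---|---|---|---|---|
| 10% | 30 | 0 | 7.5 | 15 | 22.5 |
| 20% | 60 | 0 | 15 | 30 | 45 |
| 30% | 90 | 0 | 22.5 | 45 | 67.5 |

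At p = 20%, the share of subjects shown with dose-limiting loose stools would be 60/300 = 20% if all are recorded, and (60 − 15)/300 = 15%, (60 − 30)/300 = 10% or (60 − 45)/300 = 5% otherwise. This is not the diarrhea incidence. Subjects who exceed the threshold and keep their dose would add to the recorded and the true count alike.

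**The case against.** The strongest reply is that the plan does not exclude these cases. The diarrhea sentence says if, not only if. It names a case that must be reported and bars no other. Loose stools that are not watery are arguably outside it and fall under the general definition. Subjects are told to contact the site, to report events promptly, and at each visit from Visit 2: "Subjects will be queried for any adverse events or changes to their concomitant medications". The Day 374 call asks again. An investigator who records every such case is following the protocol. Withdrawals are already covered: Section 8.2 counts failure to tolerate the medication among AEs requiring discontinuation, and 9.3.2 tabulates AEs leading to withdrawal. The eCRF is not among the documents and may collect dose changes. Finally, no decision criterion depends on the diarrhea rate.

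Most of this stands, and it limits the point. A reader might infer that diarrhea counts only above three watery stools a day, but the text does not say so. A reader might also infer that diarrhea is the main tolerability problem. The documents do not support that either: Section 5.1 says that "adverse events associated with BLI400 administered at doses required for effective treatment of constipation included flatulence, nausea, vomiting, abdominal cramping or pain and bloating", and the list in the Introduction omits diarrhea too.

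What the reply does not remove is the ambiguity. The general definition turns on whether a sign is unintended, and with a laxative a loose stool is easily read as the intended effect. A specific number will tend to guide sites, and not all in the same way. The visit queries ask about adverse events, so they carry the same ambiguity. Site contact brings the episode to staff but does not tell them to record it.

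**Conclusion.** The point holds as a gap in recording and tabulation. The trigger for halving the dose is lower than the stated reporting level for diarrhea, nothing requires the symptom behind a reduction to be entered as an AE, and no summary of reductions is planned. Diarrhea or loose stools is the only symptom for which the treatment sections provide a reduction, so the cases at risk of omission are the dose-limiting ones.

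A reader might infer that these cases will certainly be under-counted, or take the illustrative percentages as an estimate. Neither follows. The documents give neither p nor s, and s = 0 if every site applies the general AE definition. The conclusion rests on two assumptions: that some sites will treat the numeric rule as the dividing line, and that no eCRF instruction outside these documents already closes the gap. Under them the change is worth making because it is cheap and bears on the sole objective.

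**What to change.** 1. **Section 5.1.** Keep the numeric diarrhea rule for all other cases. Add one sentence: diarrhea or loose stools that leads to a dose reduction is recorded as an AE whatever the stool count, with the dose change given as the action taken.
2. **Section 9.3.2.** Add a table of subjects with a dose reduction, with its timing and reason.
3. Make the same edits in both copies of the text, and confirm that the eCRF has fields for the date of and reason for a dose change.

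Nothing further is needed for withdrawals, which 8.2 and 9.3.2 already cover.

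The cost is one sentence and one table, plus eCRF fields if they do not exist. The downside is that the reported diarrhea rate may be somewhat less favourable. The dose, the condition for reducing it and the clinical handling of subjects stay as they are; only recording and reporting change.

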9.2. Parameters to be Analyzed

The primary objective of this study is to investigate the safety of BLI400 used chronically for 12 months in subjects with constipation. Safety will be analyzed using ECG, vital signs, chemistry, hematology and urinalysis and adverse event data. Treatment emergent adverse event rates will be descriptively presented by preferred term, severity, and relationship to treatment.

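### Adverse event duration and resolution are recorded but enter no planned AE analysis, and the between-period AE test does not say whether an ongoing event counts again

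*Combined protocol and SAP*

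**What the plan says.** **Collected.** Section 5.1 lists what the investigator records for each AE. The list includes onset date and time, severity, and "duration of adverse event, and the Investigator's assessment of relationship of adverse event to study treatment". Under Section 4.2.7, the Day 374 call is to "query if any new adverse events have occurred and if any adverse events ongoing at Visit 6 have resolved".

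**Analysed.** Section 9.2 says: "Treatment emergent adverse event rates will be descriptively presented by preferred term, severity, and relationship to treatment". Section 9.3.2 adds tables by system organ class, preferred term and demographic subgroup, and a table of SAEs and AEs leading to withdrawal. Its counting rule is "Counting will be done by subject and not by event". An AE is treatment-emergent (a TEAE) if it "had an onset day and time on or after the day and time of the first dose of study drug", up to the Day 374 call. The one comparison over time reads: "The difference in adverse event rates between study periods will be tested by Chi-Square or Fisher's exact test with 95% confidence intervals".

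**Context.** The sole objective (Section 2) is the safety of chronic use. Section 9.1 justifies 300 subjects by the wish to find events that become more common or more severe with time. Of the gastrointestinal (GI) reactions in published studies, Section 5.1 says: "These adverse reactions were transient and subsided rapidly upon dose adjustment or cessation".

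The file holds the protocol text twice. Neither copy contains an AE analysis that uses duration, resolution or ongoing status.

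**The concern.** This is a single-arm study of daily dosing for a year, so the time course of AEs within the study carries much of the safety evidence. The expected GI reactions may start early and then either settle or continue for as long as dosing does. Those are different safety profiles, and a by-subject incidence table shows them alike.

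The between-period test is where the time course should appear. It depends on two rules that the plan leaves out: what the periods are, and whether an AE that began in one period and continues into the next counts in both. Two analysts could follow the text and reach opposite conclusions about the same subjects.

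**Working it through.** **Inputs.** From the documents: 300 subjects for 12 months (9.1), and clinic visits at Days 60, 120, 180, 270 and 360 (4.2.2 to 4.2.6). Not in the documents, so assumed: AE rates of 1%, 5%, 10% and 30%, and episode lengths of 3 days or about 330 days (onset around Day 30, lasting to Day 360). Section 9.1 sets the 300 by citing an exposure guideline, with no event rate or power, so there is no calculation to reproduce and no stated figure is disputed.

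**Step 1: fields collected against fields used.**

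| AE field | Collected | Used in a planned AE analysis |
|---|---|---|
| Onset | 5.1 | Yes, to define a TEAE (9.3.2) |
| Severity, relationship | 5.1 | Yes (9.2) |
| Action on participation | 5.1 | Yes, AEs leading to withdrawal (9.3.2) |
| Duration | 5.1 | No |
| Resolution after Visit 6 | 4.2.7 | No |

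**Step 2: what by-subject incidence hides.** Take a 10% rate: 300 × 0.10 = 30 subjects. Total follow-up is 300 × 360 = 108,000 subject-days.

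- Each episode lasts 3 days: 30 × 3 = 90 subject-days, or 90/108,000 = 0.083%.
- Each episode lasts 330 days: 30 × 330 = 9,900 subject-days, or 9,900/108,000 = 9.17%.

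At equal severity and relationship, both appear as 30 (10%). The 110-fold ratio is simply 330/3, so it follows from the lengths chosen. What does not depend on them is that the table is the same either way.

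**Step 3: the between-period test under two counting rules.** Compare Days 0-60 with Days 270-360. Assume full retention, no late onsets, and that every early case persists. The number of cases is x = 300 × rate. Fisher's exact test treats the two periods as independent groups of 300, so its p-values are indicative only. Because the same subjects are in both periods, the exact McNemar p-value is also shown: with x discordant subjects all in one direction it is 2 × 0.5^x.

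| Assumed rate | Counted by onset | Fisher p | McNemar p | Ongoing events included |
|---|---|---|---|---|
| 1% | 3 vs 0 | 0.25 | 0.25 | 3 vs 3 |
| 5% | 15 vs 0 | 5 × 10⁻⁵ | 6 × 10⁻⁵ | 15 vs 15 |
| 10% | 30 vs 0 | 9 × 10⁻¹⁰ | 2 × 10⁻⁹ | 30 vs 30 |
| 30% | 90 vs 0 | 6 × 10⁻³¹ | 2 × 10⁻²⁷ | 90 vs 90 |

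In the last column p = 1.00 in every row. The paired test leaves the onset-based result essentially unchanged, so the counting rule drives it, not the choice of test.

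**Step 4: relaxing two assumptions.** Keep 30 early cases and add 3 new late onsets (1%) in other subjects. By onset the comparison is 30 vs 3 whatever share of early cases persists. With ongoing events included it is 30 vs 33 if all persist (30 + 3), 30 vs 18 if half persist (15 + 3), and 30 vs 3 if none do. Only the second count responds to persistence.

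**Step 5: what PAC-SYM covers.** PAC-SYM (Appendix B) asks at Visits 1 to 6, with two-week recall, about abdominal discomfort, pain, bloating and cramps (items 1 to 4). PAC-QOL item 1 also covers bloating. Section 9.3.3 plans change from baseline and a display by severity at each visit. Among reactions named in Section 5.1, flatulence, nausea and vomiting have no PAC-SYM item. Nor does diarrhea, for which Section 5.1 sets an AE reporting threshold.

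**The case against.** A reader might infer that the planned test will report a false decline. The documents do not support that. The only onset rule in Section 9.3.2 decides whether an AE is treatment-emergent; it does not place AEs in periods. Section 3.3 describes a single 12-month Treatment Period, so even the periods are open. The false decline is one possible outcome of an incomplete instruction. This objection stands in full.

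A reader might also infer that nothing in the plan can show whether GI symptoms persist. That is too broad. PAC-SYM gives repeated measurements of bloating and abdominal pain or cramps on the visit days. They are analysed as efficacy and not linked to AE records, and they leave out the four terms in Step 5, so the objection narrows the gap without closing it.

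The severity, relationship and withdrawal tables will separate some persistent cases. They will not separate a mild or moderate reaction that a subject tolerates for a year without withdrawing.

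The remark that reactions are transient is background about published studies, not a hypothesis this trial undertakes to test. New-onset counts and severity tables also bear directly on the purpose stated in Section 9.1. Both points are fair. Even so, events that accumulate because they do not resolve are part of chronic-use safety, and new-onset counts miss them.

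Finally, the illustration uses chosen inputs, and at 1% the apparent decline is not significant. That also stands: the problem concerns common terms.

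**Conclusion.** The point holds in a limited form. Duration and resolution are collected and left out of every planned AE analysis, so AE incidence cannot distinguish brief from year-long reactions of the same term, severity and relationship. This is certain from the text and needs no assumption. It matters most for flatulence, nausea, vomiting and diarrhea.

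The second part is conditional. The between-period test lacks a definition of its periods and a rule for ongoing events. If AEs are placed by onset, an early persistent reaction appears to go away, by 15 to 90 subjects of 300 at assumed rates of 5% to 30%, and by 3 subjects at 1%. These sizes rest on full retention, no late onsets and complete persistence; Step 4 shows that the mechanism survives some late onsets and partial persistence. No figure in the plan is wrong. This is a cheap improvement to analyses that serve the study's only objective.

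**What to change.** In Section 9.3.2:

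1. Define the study periods by the visit intervals: Days 0-60, 60-120, 120-180, 180-270 and 270-360, each closed by its visit. Show TEAEs starting after Visit 6 in a separate follow-up row.
2. For any AE, the GI system organ class and the expected GI terms, report in each interval (a) subjects with a new-onset TEAE and (b) subjects with a TEAE present at any time. Use subjects still on BLI400 as the denominator. The last two intervals are 90 days and the others 60, so give new onsets per unit of exposure as well. Read these tables beside the withdrawal table, because prevalence among those still treated also falls when affected subjects leave.
3. Compare periods with a method for paired data, such as McNemar's test or a repeated-measures model.
4. Add time to resolution with unresolved events censored, and the number unresolved at the follow-up call. Note that this call falls after dosing ends, so resolution then does not show that a reaction settles on treatment.

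The cost is a few extra tables and their programming, from fields already in the AE record. Duration will be less precise for intermittent symptoms such as flatulence, with visits two to three months apart, so the count of subjects with the event present in each interval should carry the main weight.
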